#### **V.1. Sensitivity Analysis for Missing Data**

Baseline characteristics of patients with missing primary outcome will be compared with the baseline characteristics of those included in the analysis to assess potential for bias based on these missing values.

The primary analysis will use complete data, excluding individuals without outcome data. To assess the potential for bias incurred by ignoring the missing data, we will conduct a sensitivity analysis under the assumption of missing at random (MAR) using the inverse-probability-weighting (IPW) method (Hogan and Lancaster, 2004). In the calculation of the M-H RR and test statistic, each subject will be weighted by the inverse probability of being a complete case. We will use the non-missing rate of the primary outcome within each treatment and each stratum to estimate this probability.

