## **IV. General Principles**

All analyses (primary, secondary, exploratory) will adjust for the 2 binary stratification factors, namely sex, fracture type (intracapsular, extracapsular), and country (U.S., Canada sites). Sex, fracture type, and site were the original stratification factors for randomization assignment, but with 46 participating sites, some with very few enrolled subjects, it will not be possible to include site in the stratified analysis. Because there might be systematic differences in health care and insurance use between Canada and U.S. sites, we will add country as an additional stratification factor. We will perform descriptive analyses of results by site to see whether there appear to be any major site-specific effects. Analyses will follow a modified intention-to-treat principle, with sensitivity analyses performed to assess the potential impact of missing values and noncompliance. Subjects who had randomization codes generated due to purely technical errors in operating the database will be excluded from any analysis. Subjects who died before receiving either study treatment will also be excluded from any analysis. Subjects randomized and later found not to meet eligibility criteria will be included in the primary analysis to avoid potential bias due to differential assessment of eligibility. Sensitivity analyses excluding these subjects will be conducted. Subjects who were randomized into the wrong stratum will be analyzed as per-randomization strata. All analyses will use 2-sided tests and an overall significance level of 0.05 as the threshold for statistical significance. We will report nominal p-values for all analyses.

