## **V. Primary Outcome Analysis**

The primary endpoint of the study is whether or not the subject is alive and capable of walking 10 feet or across a room without human assistance at 60 days post-randomization. As per the study protocol, the day 60 assessment will be performed within a window of 31-90 days post-randomization, although every effort will be made to make the assessment as close to day 60 as

possible. Results of assessments performed outside the 31-90 day window will be considered as missing data. The treatment effect will be evaluated using the Mantel-Haenszel (MH) test for difference in proportions, stratified by sex, fracture type, and country. The MH relative risk (RR) of spinal anesthesia (SA) vs. general anesthesia (GA) will be reported. *The Breslow-Day test* (Breslow and Day, 1980) will be used to test homogeneity of the RRs across strata. If there is statistically significant heterogeneity, we will report separate RRs within strata.

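### The missing-data sensitivity analysis puts inverse-probability weights into the Mantel-Haenszel test statistic with no matching variance, so done as written its p-value is usually too small

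*SAP*

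**What the plan says.** The primary test is set in SAP section V: "The treatment effect will be evaluated using the Mantel-Haenszel (MH) test for difference in proportions, stratified by sex, fracture type, and country". With three two-level factors this gives 8 strata. Section V.1 keeps the primary analysis unweighted: "The primary analysis will use complete data, excluding individuals without outcome data".

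Section V.1 then adds one re-analysis for missing outcomes: "we will conduct a sensitivity analysis under the assumption of missing at random (MAR) using the inverse-probability-weighting (IPW) method". It says where the weights go: "In the calculation of the M-H RR and test statistic, each subject will be weighted by the inverse probability of being a complete case". It also says how they are obtained: "We will use the non-missing rate of the primary outcome within each treatment and each stratum to estimate this probability".

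Neither V.1 nor any other section names a robust, bootstrap or otherwise adjusted variance for the weighted test. Section IV sets the threshold, "All analyses will use 2-sided tests and an overall significance level of 0.05 as the threshold for statistical significance", and commits to reporting nominal p-values for every analysis, so the weighted p-value will be reported.

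**The concern.** A weight of 1/(response rate) makes each observed patient stand in for the missing patients of the same arm and stratum. That is suitable for estimating a risk. It is not suitable for measuring precision, because no information has been gained on the missing patients. The Mantel-Haenszel variance is computed from cell counts. If the counts are the weighted ones, the variance is that of a trial with no missing outcomes.

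At stake is the meaning of the only missing-data re-estimation that V.1 specifies. The weights are constant within arm and stratum, so the stratum-specific risks do not change, and the relative risk moves only through the relative contribution of the strata. The p-value is therefore the main thing that changes, and it tends to look stronger as more data are missing. A primary result just above 0.05 could fall below 0.05 in its own sensitivity analysis for this reason alone.

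**Working it through.** **Inputs from the SAP.** Two-sided 0.05 (section IV); stratified Mantel-Haenszel test with 8 strata (section V); weight equal to 1/(non-missing rate) per arm and stratum, applied to the relative risk and the test statistic (section V.1). The SAP gives no sample size, event rate or missing rate, so there is no planned figure to reproduce. Those inputs below are assumptions.

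**Step 1: weighted counts.** Suppose a cell has n eligible patients, of whom o are observed. Each observed patient gets weight n/o, and the weighted total is o × (n/o) = n.

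**Step 2: effect on the statistic.** In each stratum let n1 and n0 be the arm totals, a the events in the first arm, M all events and T = n1 + n0. The statistic is

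chi-square = [Σ(a − n1·M/T)]² / Σ[n1·n0·M·(T − M) / (T²(T − 1))].

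With a common response rate r, weighting multiplies every count by 1/r. The squared numerator grows by 1/r². The variance grows by (1/r⁴)/(1/r³) = 1/r, apart from the minus 1 in T − 1. The chi-square is therefore inflated by about 1/r and Z by 1/√r.

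**Step 3: true error rate.** With missing rate m = 1 − r, type I error = 2·[1 − Φ(1.96·√(1 − m))].

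| Assumed missing | Z inflation | True type I error | Reported value when the correct p is 0.050 |
|---|---|---|---|
| 2% | 1.010 | 0.052 | 0.048 |
| 5% | 1.026 | 0.056 | 0.044 |
| 10% | 1.054 | 0.063 | 0.039 |
| 15% | 1.085 | 0.071 | 0.034 |
| 20% | 1.118 | 0.080 | 0.028 |
| 30% | 1.195 | 0.101 | 0.019 |

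Example: a complete-case p of 0.060 is Z = 1.881. If the contrast itself does not move, 90% response gives 1.881/√0.90 = 1.983, p = 0.047. At 85% response it is 1.881/√0.85 = 2.040, p = 0.041.

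**Step 4: simulation.** 8 strata, no treatment effect, event risk 0.12 to 0.28 across strata, 100,000 replicates per scenario. Rejection rates at nominal 0.05 are shown for assumed N = 800 / 1,600.

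| Missing (general / spinal) | Complete-case MH | MH on weighted counts | Weighted contrast, variance from observed patients |
|---|---|---|---|
| 0% / 0% | 0.0486 / 0.0496 | 0.0486 / 0.0496 | 0.0486 / 0.0496 |
| 5% / 5% | 0.0499 / 0.0516 | 0.0562 / 0.0578 | 0.0498 / 0.0514 |
| 10% / 10% | 0.0512 / 0.0492 | 0.0649 / 0.0627 | 0.0509 / 0.0494 |
| 5% / 15% | 0.0493 / 0.0502 | 0.0626 / 0.0635 | 0.0494 / 0.0501 |
| 20% / 20% | 0.0489 / 0.0491 | 0.0802 / 0.0786 | 0.0490 / 0.0491 |
| 10% / 30% | 0.0499 / 0.0512 | 0.0824 / 0.0826 | 0.0497 / 0.0510 |

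The simulation agrees with the formula. Changing only the variance restores the level. Where outcomes were missing, the median absolute difference between the weighted and complete-case log relative risk was 0.001 to 0.006, so the estimate hardly moves.

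**The case against.** The strongest reply is that V.1 names no variance at all. It does not call the weights frequency weights, and a weighted contrast with a robust variance would also fit its sentence. A reader might infer that the SAP commits the sponsor to the wrong variance, and the text does not go that far. What stands is that V.1 puts the weights into the test statistic itself and gives no correction. Entering weighted counts in the usual Mantel-Haenszel formula follows the text literally and produces the error.

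Other stronger readings also fail:

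- **That the p-value always shrinks.** Reweighting shifts the strata a little. In simulated null trials the weighted p-value was larger than the complete-case one in about 9% to 27% of runs, depending on the assumed size and response. Where the complete-case p was 0.05 to 0.10, this happened in at most 6%.
- **That the fault lies in inverse-probability weighting as such.** It comes from the scale of the weights. Rescaling them to the observed number in each stratum brought the type I error of the same formula back to 4.7% to 5.4%.
- **That the weighted total is everyone randomised.** It is everyone eligible for analysis. Section IV excludes randomisation codes generated by technical error and deaths before study treatment.
- **That a planned confidence interval is too narrow.** V.1 mentions no interval for this analysis. One computed from the weighted table would be too narrow, but that is conditional.

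It is also fair to say that the weighted analysis is meant to assess bias, that no decision rule rests on its p-value, and that the result changes from non-significant to significant in few null trials: about 0.6% to 1.2% at 95% response, 1.4% to 1.9% at 90% and 2.1% to 2.9% at 85%. This limits the consequence but does not make the p-value correct.

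**Conclusion.** The point holds as a flaw in a sensitivity analysis. On its plain reading, V.1 prescribes a weighted test whose variance counts missing outcomes as observed. The size depends entirely on the missing rate, which the SAP does not give: negligible at 2%, small at 5%, and material at 10% to 20%. Section V treats assessments outside days 31 to 90 as missing, and the SAP sets no ceiling on missingness, so the larger rates cannot be excluded from the document.

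A reader might infer that the trial's main conclusion is at risk. It is not: the primary test is an unweighted complete-case analysis and kept its level (0.049 to 0.052) in every simulated scenario. The analytic figures assume a common response rate and large-sample normality; the simulated scenarios with unequal response by arm gave similar results.

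**What to change.** Amend V.1 to keep the weights for the relative risk and to name the variance for the test and for any confidence interval. Suitable choices are:

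- a sandwich variance for the weighted log relative risk; or
- a bootstrap within arm and stratum that re-estimates the weights in each resample; or
- weights rescaled to sum to the observed number in each stratum before the Mantel-Haenszel formula is applied.

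Add that unscaled weighted counts are not to be entered as frequencies in the Mantel-Haenszel chi-square. The cost is one or two sentences and a few lines of code. The sensitivity p-value will usually be slightly less favourable.

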The walking ability component of the primary outcome will be assessed by a telephone interview with the subject conducted as close to day 60 as possible; information obtained during a 31-90-day window after randomization will be considered acceptable for analysis. To assess walking ability, respondents were asked to indicate whether on average in the 7 days prior to the interview they used/received human assistance to ambulate. Individuals indicating that they did not ambulate at all over the 7 days preceding the interview were coded as having met the study outcome. Vital status will be assessed at the day 60 telephone interview; for patients who cannot be reached for the 60-day telephone interview, vital status at 60 days will be assessed via telephone follow up at subsequent time points. Additional information on deaths prior to day 60 will be obtained from site Adverse Event reports and via a National Death Index search for patients who were randomized at US sites and for whom sufficient identifying information is available. Patients who are known to have died by day 60 will be assessed as having met the primary outcome, regardless of walking status assessments prior to that point. Those known to be alive at day 60 but without a response to the question about capability of walking 10 feet will be considered to be missing the primary outcome. In cases where patients were unable to provide their own responses to the primary outcome assessment (e.g., due to dementia or acute illness), data were collected from alternate (proxy) respondents as described in the main study protocol. Subjects for whom information on both components of the primary endpoint are missing (i.e., patient has become lost to follow-up so that neither survival status nor walking ability is known) will be excluded from the primary analysis, but a variety of sensitivity analyses, described below, will be conducted to assess the potential influence of these exclusions on the comparison of outcomes.

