#### **VIII. Subgroup Analyses**

We will evaluate treatment difference in the subgroups defined by the following stratification variables:

- a. Sex: Male vs. Female, defined as per stratification
- b. Fracture type: Femoral neck vs intertrochanteric/subtrochanteric, defined as per stratification
- c. Country of enrollment: Canada vs US
- d. Need for assistive devices to ambulate prior to fracture: present vs. absent
- e. Age category: “oldest old” (85 years and over) vs all others
- f. History of Alzheimer’s disease or other dementia: present vs absent
- g. History of chronic obstructive pulmonary disease or asthma: present vs absent
- h. History of coronary artery disease or prior myocardial infarction: present vs absent
- i. Community residence prior to fracture: home or independent living retirement home vs nursing home, rehabilitation or acute care hospital vs other.

The first step will be to test for interaction between treatment and variable defining the subgroups. Analysis within subgroups will be performed for any variable showing an interaction yielding a p-value of 0.20 or less. Subgroup analyses will be analyzed similarly as for primary analysis.

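### The V.1 weights are constant within each arm-by-stratum cell, so the missing-data sensitivity analysis cannot reveal bias within strata; the variance of its weighted test is also not stated

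*SAP*

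**What the plan says.** SAP V makes the primary comparison a Mantel-Haenszel "test for difference in proportions, stratified by sex, fracture type, and country", using complete cases. The sentence in that section that begins "Those known to be alive at day 60 but without a response to the question about capability of walking 10 feet will be considered" classes such survivors as missing. Subjects for whom "neither survival status nor walking ability is known" are excluded, and the section promises several sensitivity analyses for these exclusions. Known deaths by day 60 always count as having met the outcome, so they are never missing.

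V.1 then gives two things. The first is descriptive: "Baseline characteristics of patients with missing primary outcome will be compared with the baseline characteristics of those included in the analysis". The second is one quantitative analysis under missing at random: "In the calculation of the M-H RR and test statistic, each subject will be weighted by the inverse probability of being a complete case". The probability is specified in a single sentence: "We will use the non-missing rate of the primary outcome within each treatment and each stratum to estimate this probability". No baseline variable other than the strata enters the weights, and no variance for the weighted estimate or test is named.

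**The concern.** Weighting changes an estimate only if the weights differ among the subjects being averaged. Here they are equal for everyone in a given arm and stratum, and the primary analysis already computes its risks within those cells. The weighting therefore leaves the within-stratum comparison untouched.

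V.1 offers this analysis as the check on bias from ignoring missing data, and it is the only quantitative one there. If response depends on prognostic features within strata, the check will still agree with the primary result, and that agreement can be read as reassurance it does not provide.

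Two smaller matters come with it. The weights also enter the test statistic, and without a stated variance the p-value is undefined or, on the most direct reading, too small. The same cell weight is also given to known deaths, who cannot be missing, and to survivors, who can.

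**Working it through.** **Inputs.** From the SAP: the weight definition (V.1); the strata sex × fracture type × country, 2 × 2 × 2 = 8 (V); two-sided 0.05 (IV). The SAP gives no sample size, event risk or response rate, so there is no figure of its own to reproduce. Assumed: 1,600 subjects, 8 strata, event risk 14–26%, response 80–95%.

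**1. Algebra (no assumption needed).** Take a cell with N subjects in the analysis population, n with an observed outcome and a events. Each weight is w = N/n. The weighted risk is (a·w)/(n·w) = a/n, the complete-case risk. Numerically, the largest cell difference was below 1e-16.

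The pooled estimate is RR = Σ W_s·p1_s / Σ W_s·p0_s, with W_s = n1_s·n0_s/(n1_s + n0_s). The weighting changes only W_s. If the stratum RRs are equal, the pooled RR does not change at all. With missingness random within strata, the weighted and complete-case RRs differed by a median of 0.1–0.2% (95th percentile 0.3–0.7%) at 95–80% response.

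**2. Missingness related to dementia, no true effect.** Assume 15% have dementia, with risk 2.5 times the stratum base with it and 0.8 times without. Response is 92% without dementia and 90% in general-anesthesia (GA) dementia patients; it varies in spinal (SA) dementia patients. At 70% in the latter, in units of base risk:
- GA: (0.15×0.90×2.5 + 0.85×0.92×0.8)/(0.135 + 0.782) = 0.9631/0.917 = 1.0503
- SA: (0.15×0.70×2.5 + 0.85×0.92×0.8)/(0.105 + 0.782) = 0.8881/0.887 = 1.0012
- RR = 1.0012/1.0503 = 0.953

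| SA dementia response | Complete-case RR | Planned weighted RR | Weights including dementia |
|---|---|---|---|
| 90% | 1.000 | 1.000 | 1.000 |
| 85% | 0.989 | 0.989 | 1.000 |
| 80% | 0.977 | 0.977 | 1.000 |
| 70% | 0.953 | 0.953 | 1.000 |

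With equal response by arm there is no bias under the null.

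**3. Equal response by arm, effect differing by dementia.** Assume RR 0.70 with dementia and 1.0 without. The full-data RR is (0.15×2.5×0.70 + 0.85×0.8)/(0.15×2.5 + 0.85×0.8) = 0.9425/1.055 = 0.893. At 90/80/70% dementia response, complete-case and planned weighted RR are both 0.895/0.903/0.911.

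**4. Where the planned weights do work.** With RR 1.0 in US strata and 1.5 in Canadian strata, and response 90% and 70% respectively, the full-data RR is 1.107, complete-case 1.087 and planned weighted 1.107.

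**5. Variance.** Weighted counts restore the full cell size, so the ordinary MH chi-square grows by about 1/r, where r is the response rate. A nominal 5% test then has type I error of about 2·(1 − Φ(1.96·√r)).

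| Response | Chi-square ratio | Theory | Simulated, weighted counts | Simulated, complete case |
|---|---|---|---|---|
| 95% | 1.05 | 0.056 | 0.057 | 0.051 |
| 90% | 1.11 | 0.063 | 0.064 | 0.051 |
| 85% | 1.18 | 0.071 | 0.072 | 0.050 |
| 80% | 1.25 | 0.080 | 0.082 | 0.052 |

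The simulation used 40,000 null trials per row. A bootstrap that re-estimates the weights gave 0.048 at 90% and 0.046 at 80% response (3,000 trials, 300 resamples).

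**6. Deaths.** Assume 4% dead, 15% of survivors not walking, and survivor missingness of 16% in one arm and 8% in the other. With all deaths known:
- first arm: (0.04 + 0.96×0.84×0.15)/(0.04 + 0.96×0.84) = 0.16096/0.8464 = 0.1902
- second arm: (0.04 + 0.96×0.92×0.15)/(0.04 + 0.96×0.92) = 0.17248/0.9232 = 0.1868
- RR = 1.018, although the true RR is 1.000

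With 90% and 80% of deaths known it is 1.017 and 1.015. With equal survivor missingness by arm it is 1.000.

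**The case against.** **The planned weights are not idle.** When effect and response both vary by country, they recover the full-data RR (step 4). The SAP adds country because of possible systematic differences and tests homogeneity across strata. Step 3 has the same structure with dementia in place of country. This stands: the exact identity holds for cell risks and stratum RRs, not for the pooled RR. It does not help with any factor outside the strata.

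**The dementia gap is assumed.** Section V uses proxy respondents when patients cannot answer, and names dementia as an example. That should reduce the loss, and no SAP figure supports a 20-point gap between arms; at 5 points the bias is 1.1%. This limits the likely size. Proxies do not prevent loss to follow-up, though, and they do not enter the weights.

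**The baseline comparison would show imbalance.** It may. It is descriptive, however, and gives no adjusted estimate.

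**The ordinary variance is not prescribed.** Correct: the SAP is silent, so the inflated error rates are conditional on that reading. They concern a sensitivity p-value only.

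**The death point is small, and death ascertainment is uneven**, because the National Death Index search covers US sites only. Both are true. It is a refinement and does not carry the concern.

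**Stratum in V.1 might include site.** Weights would then vary within analysis strata. Section IV makes this unlikely, because it leaves site out of the stratified analysis, and patient-level predictors would still be ignored.

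**Conclusion.** The concern holds. It follows from algebra alone that the planned weights leave every cell risk and stratum RR at its complete-case value, so within-stratum bias from missing data can be neither seen nor corrected.

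The practical size depends on figures the SAP does not give. Under the dementia assumptions the uncorrected null bias is 0% with equal response by arm, rising to 4.7% (RR 0.953) at a 20-point difference in response among dementia patients. With effect modification and equal response by arm, the RR moves from 0.893 to at most 0.911 over the range tried. The variance omission would matter only if weighted counts enter the ordinary MH statistic, where type I error is about 5.6–8.0% at 95–80% response. Death weighting adds at most about 1.8% in the cases tried.

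The primary complete-case test is not altered. This should be fixed because the sensitivity analysis does not do what V.1 offers it for, and the remedy is cheap.

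**What to change.** Replace the cell response rate in V.1 with a logistic model for response. Include treatment, sex, fracture type, country and baseline variables the SAP already uses in section VIII: age, dementia, residence, and the item "Need for assistive devices to ambulate prior to fracture: present vs. absent".

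Fit the model among subjects not known to have died by day 60, and give known deaths weight 1. State that this is approximate, since some subjects with unknown vital status may have died.

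Name the variance: a robust or bootstrap standard error and p-value that re-estimates the weights, not the ordinary MH statistic on weighted counts. State that the analysis still assumes missing at random.

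The cost is SAP wording and a few lines of code, with no new data and no change to the primary analysis. The sensitivity interval will be slightly wider, and outcome-dependent missingness will still not be covered.
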